# 9.1.5. Secondary efficacy endpoints:

To assess whether the ORR to CB-103 in combination with Venetoclax is dependent on pretreatment expression of Notch and/or BCL2 pathway, patients will be stratified according to the pre-treatment presence or absence of Notch and BLC2 expression. ORR will be evaluated in each of the four strata.

For each subject, minimal residual disease (MRD, presence of leukemic cells below the threshold of detection by conventional morphologic methods), duration of response, event-free survival, and overall survival will be calculated.

The depth of remission, i.e. detection of MRD, will be evaluated by PCR/NGS methods that can detect leukemic cells at a sensitivity threshold of at least  $1 \times 10^{-6}$  bone MNCs. Flow cytometry and/or molecular analysis with PCR methods that can detect leukemic cells at a sensitivity threshold of at least  $1 \times 10^{-4}$  bone marrow nuclear cells (MNCs) will also be performed.

The duration of response is defined as the number of days from the date of initial response (PR or better) to the date of first documented disease progression/relapse or death, whichever occurs first. Event-free survival is defined as the number of days from the date of treatment initiation (i.e., C1D1) to the date of documented treatment failure, relapses from CR, or death from any cause, whichever occurs first, and will be calculated for all patients. In the event that neither disease progression nor death is documented prior to study termination, analysis cutoff, or the start of confounding anticancer therapy, these endpoints will be censored at the date of last tumor assessment date. Overall survival is defined as the number of days from study enrollment to death due to any cause.

#### 9.1.6. Exploratory endpoints:

- **9.1.6.1.** CB-103 plasma concentrations, PK parameters (e.g., Cmax and AUC0-8) vs safety and/or efficacy
- **9.1.6.2.** PD parameters, as for instance Notch and BCL2 expressionin pre- and post-treatment marrow samples.
- **9.1.6.3.** the number and percentage of patients that are able to transition to HSCT in: **9.1.6.3.1.** Either in the patients achieving CR after the induction and reinduction cycles;
  - **9.1.6.3.2**. Or in the patients with PR or stable disease (SD) after the induction and reinduction cycles.

#### 9.2. Primary Safety Endpoints:

**9.2.1. Primary Safety Analysis**: The incidence rate, severity and relationship to CB-103 and/or venetoclax of adverse drug reactions and serious drug reactions according to common terminology criteria for adverse events (CTCAE) NCI CTCAE version 5.0.

Page | 39 04/25/2024

The overall incidence and severity of all adverse events using Common Toxicity Criteria v 4.0.

#### 9.2.2. Safety Definitions:

#### 9.2.2.1. Adverse Event (AE):

An Adverse Event is defined as any untoward medical occurrence in a patient regardless of its causal relationship to study treatment. An AE can be any unfavorable and unintended sign (including any clinically significant abnormal laboratory test result), symptom, or disease temporally associated with the use of the study treatment, whether or not it is considered to be study drug(s) related. Included in this definition are any newly occurring events and any previous condition that has increased in severity or frequency since the administration of the study.

**Attribution** - the determination of whether an adverse event is related to a medical treatment or procedure.

- Definite the adverse event is clearly related to the investigational agent(s).
- **Probable** the adverse event is likely related to the investigational agent(s).
- **Possible** the adverse event may be related to the investigational agent(s).
- Unlikely The adverse event is doubtfully related to the investigational agent(s).
- Unrelated The adverse event is clearly NOT related to the investigational agent(s)

Medical conditions/diseases present before starting study drugs are only considered adverse events if they worsen after starting the study drug. Abnormal laboratory values or test results constitute adverse events only if they induce clinical signs or symptoms, are considered clinically significant or require therapy.

The severity of the adverse events (AEs) -The severity of the adverse events (AEs) will be graded according to the **National Cancer Institute Common Terminology Criteria for Adverse Events (NCI CTCAE) V**5.0. Events not included in the NCI CTCAE will be scored as follows:

General grading:

- **Grade 1:** Mild: discomfort present with no disruption of daily activity, no treatment required beyond prophylaxis.
- Grade 2: Moderate: discomfort present with some disruption of daily activity, require treatment.
- **Grade 3:** Severe: discomfort that interrupts normal daily activity, not responding to first line treatment.
- Grade 4: Life Threatening: discomfort that represents immediate risk of death

RedCap will be used as the electronic Case Report Form (eCRF). The Investigator (or physician designee) is responsible for verifying and providing source documentation for all adverse events and assigning the attribution for all adverse events for subjects enrolled.

Adverse events will be captured per the phase II recommended guidelines

 Signs and symptoms relating to adverse event diagnoses will not be captured as individual events. (e.g. event of catheter related infection: redness, pain, swelling

Page | 40 04/25/2024

- at catheter site are signs and symptoms of the catheter related infection and thus will not be recorded as individual events).
- The maximum grade of the adverse event (AE) will be captured per course or protocol defined visit date. The start date will be recorded as when the AE first began or worsened from baseline, regardless of when the event was at its highest grade.
- An AE will be recorded as intermittent if the AE is not continuous but reoccurs at an irregular interval within a course.
- Hematologic adverse events will not be recorded or reported for studies in patients with any type of leukemia and/or related disorders, except for:
  - a. Prolonged myelosuppression as defined by marrow hypocellularity on day 42 or later (6 weeks) from start of therapy without evidence of leukemia (< 5% blasts).
  - b. Hematologic events that result in dose modifications, interruptions or meets the protocol definition of DLT or SAE.
- Abnormal laboratory values or test results will not be recorded or reported as adverse events unless it leads to therapeutic intervention, results in dose modification or interruption, or meets the protocol definition of a DLT or SAE.

Only the following AEs from the Adverse Event Record will be reported in the CRF:

- Any grade adverse event that is possibly, probably, or definitely related to the study drug(s).
- All serious adverse events regardless of attribution to the study drug(s).
- Any grade adverse event regardless of attribution to the study drug(s) that results in any dose modification.

The investigator (or physician designee) is responsible for verifying and providing source documentation for all adverse events and assigning the attribution for all adverse events for subjects enrolled. For non-MD Anderson laboratory results, the principal investigator (or physician designee) will review laboratory results, and sign and date the results.

Table 17: Recommended Adverse Event Recording Guidelines

Attribution	Grade 1	Grade 2	Grade 3	Grade 4	Grade 5
Unrelated	Phase I	Phase I	Phase I Phase II	Phase I Phase II Phase III	Phase I Phase II Phase III
Unlikely	Phase I	Phase I	Phase I Phase II	Phase I Phase II Phase III	Phase I Phase II Phase III
Possible	Phase I Phase II	Phase I Phase II Phase III			

Page | 41 04/25/2024

	Phase I	Phase I	Phase I	Phase I	Phase I
Probable	Phase II	Phase II	Phase II	Phase II	Phase II
		Phase III	Phase III	Phase III	Phase III
	Phase I	Phase I	Phase I	Phase I	Phase I
Definitive	Phase II	Phase II	Phase II	Phase II	Phase II
		Phase III	Phase III	Phase III	Phase III

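### The all-adverse-events part of the primary safety analysis cannot be produced from the CRF, which also omits non-serious unrelated grade ≥3 events that Table 17 marks for Phase II

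*Combined protocol and SAP*

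**What the plan says.** Section 9.2.1 has two parts. The first is "The incidence rate, severity and relationship to CB-103 and/or venetoclax of adverse drug reactions and serious drug reactions", graded by CTCAE version 5.0. The second is "The overall incidence and severity of all adverse events using Common Toxicity Criteria v 4.0". Section 9.2.2.1 defines an adverse event as "any untoward medical occurrence in a patient regardless of its causal relationship to study treatment" and grades severity by CTCAE v5.0.

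Section 9.2.2.1 also sets the collection rules. It states "Adverse events will be captured per the phase II recommended guidelines", and Table 17 gives those guidelines by attribution, grade and phase. For unrelated and unlikely events, Phase II appears at grades 3, 4 and 5 but not at grades 1 and 2. The CRF rule follows: "Only the following AEs from the Adverse Event Record will be reported in the CRF". Three categories are listed: possibly, probably or definitely related events of any grade; serious events of any attribution; and "Any grade adverse event regardless of attribution to the study drug(s) that results in any dose modification".

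Two further rules in that section apply whatever the attribution. Haematologic events are not recorded, apart from prolonged myelosuppression and events that change dosing or meet the DLT or SAE definition. Laboratory abnormalities are not recorded unless they lead to intervention, change dosing or meet the DLT or SAE definition.

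Section 12 separately defines the primary toxicity endpoint used for monitoring: grade ≥3 non-haematological events possibly or probably related to study drug, in the 28-day induction cycle.

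**The concern.** Safety and tolerability is the first primary objective (section 1.1.1), and part of its analysis is defined on a set of events wider than the one the CRF holds. No section names another data source for that part or narrows the word all.

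The practical stake is a check on attribution. The trial has one arm, so there is no control rate against which to judge whether an event was drug-related, and the section 12 endpoint counts only events the investigator attributes to study drug. An all-cause grade ≥3 rate beside the attributed rate would show how far the conclusion depends on those judgements. As the CRF list stands, the database lacks some of the events needed to compute it.

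**Working it through.** **Step 1. Compare the rules, before the haematologic and laboratory exclusions.**

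| Event | 9.2.1, second part | Table 17, Phase II | CRF list |
|---|---|---|---|
| Related, any grade | counted | recorded | yes |
| Unrelated or unlikely, serious or dose-modifying | counted | recorded from grade 3 | yes |
| Unrelated or unlikely, not serious, no dose change, grade 1–2 | counted | not recorded | no |
| Unrelated or unlikely, not serious, no dose change, grade ≥3 | counted | recorded | **no** |

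The last two rows are why the second part of 9.2.1 cannot be produced from the CRF. The last row is also where the CRF list falls short of Table 17. The haematologic and laboratory exclusions narrow the collected set further, so even the wider adverse event record would not give all events.

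**Step 2. Check whether the decision rule is affected.** The section 12 endpoint counts related grade ≥3 events, a subset of the first CRF category, so the list removes nothing from it. As background, the section 12 figures were recomputed. The Dirichlet prior (0.05, 0.1, 0.15, 0.7) gives marginals Beta(0.15, 0.85) for efficacy and Beta(0.2, 0.8) for toxicity. With cutoffs 0.57(n/30)^0.86 and 0.57(n/30)^(0.86/3), the Table 18 boundaries reproduce exactly:

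- n = 10: stop at ≤0 responses or ≥3 toxicities
- n = 20: ≤2 or ≥5
- n = 30: ≤5 or ≥6

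Exact enumeration gives a 78.46% chance of claiming the treatment acceptable in scenario 3 (Table 19: 77.76%) and 8.17% in scenario 6 (Table 19: 8.34%). All ten rows agree within about 0.7 points. None of these figures depends on the omitted events.

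**Step 3. Size the grade ≥3 gap.** The only figures in the documents are from the first-in-human study (section 2.3.2): 699 events, 285 of them related (41%), with 11% of events at grade ≥3.

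- Not related: 699 − 285 = 414, and 414/699 = 59%.
- Assuming the 11% applies equally to the unrelated events: 0.11 × 414 = 45.5, about 46, and 45.5/699 = 6.5%.
- Without that assumption: grade ≥3 events total 0.11 × 699 ≈ 77. This is fewer than either 285 or 414, so the number unrelated could lie anywhere from 0 to 77 (0% to 11% of all events).

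All of these are before serious and dose-modifying events, which do reach the CRF, are removed.

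**Step 4. What the missing rate could inform.** At 30 patients, 5 toxicities (5/30 = 17%) is acceptable and 6 (6/30 = 20%) is not. At that margin, reclassifying one patient changes the reading under the non-binding criteria.

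**The case against.** The strongest reply is that section 9.2.2.1 describes two layers. Table 17 governs what is captured in the adverse event record, and the CRF list governs what is transferred from it. On that reading Table 17 and the CRF list do not strictly conflict, and unrelated grade ≥3 events can be recovered from source. This stands as far as it goes, and it is why the fix is cheap. It does not supply the endpoint, because no section provides for the untransferred events to be analysed. Section 10.4.3 plans monitoring of 30% of subjects, and section 10.4.7 has monitors compare key eCRF entries with source.

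A second reply is that most severe events arrive by another route. Deaths, life-threatening events and hospitalisations are serious under section 9.2.2.2. Table 13 attaches a dose action to grade 3 and 4 non-laboratory events without reference to attribution, although its heading limits it to after cycle 1 while section 6.1 opens by referring to cycle 1 and beyond. This also stands. The residual gap at grade ≥3 is mainly non-serious, unrelated or unlikely grade 3 events without a dose change.

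A reader might infer that more than half of adverse events are lost, from the 59% in the first-in-human study. The documents do not support using that figure as the size of the problem. It covers all grades, only 11% of that study's events were grade ≥3, and Table 17 does not ask a Phase II trial to record unrelated grade 1–2 events. That study also enrolled patients with solid tumours as well as haematological malignancies.

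**Conclusion.** The inconsistency is in the text and does not depend on any figure. The second part of the 9.2.1 primary safety analysis cannot be produced from the CRF, and the CRF list omits a class of grade ≥3 events that Table 17 marks for Phase II.

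A reader might go further and infer that the whole primary safety endpoint, or the toxicity stopping rule, is compromised. Neither follows. The drug-reaction part of 9.2.1 and the section 12 endpoint rest on events within the CRF list, and the BOP2 boundaries and operating characteristics are unchanged. What is lost is a complete overall summary and the means to test sensitivity to attribution.

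The size at grade ≥3 is at most about 6.5% of events if the first-in-human grade split holds among unrelated events, or 0% to 11% without that assumption, in both cases before removing serious and dose-modifying events. The population and the drug combination differ from that study, so these figures are only a guide. The two CTCAE versions in 9.2.1 are a separate wording slip that the same amendment can correct.

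**What to change.** 1. Add a fourth category to the CRF list in section 9.2.2.1: *any grade ≥3 adverse event regardless of attribution, subject to the haematologic and laboratory exclusions above*. This brings the list into line with Table 17 at grade ≥3.
2. Restate the second part of 9.2.1 as the events actually collected: all related, all serious, all dose-modifying and all grade ≥3 events, with the same two exclusions written in. Without them the restated endpoint would again promise more than is recorded.
3. Grade by CTCAE v5.0 only, in line with section 9.2.2.1.
4. In section 12, report the cycle-1 grade ≥3 non-haematological rate regardless of attribution as a sensitivity analysis beside the attributed rate. Leave the stopping boundaries as they are.

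The cost is one extra CRF category, slightly more data entry and a protocol wording change. Under Table 17 the added events should already be in the adverse event record. Unrelated or unlikely grade 1–2 events that are neither serious nor dose-modifying would remain uncollected, and the restated 9.2.1 would make that clear.

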# 9.2.2.2. Serious Adverse Event or Serious Adverse reaction (SAE) Reporting Requirements for M D Anderson Sponsor IND:

An adverse event or suspected adverse reaction is considered "serious" if, in the view of either the Investigator or the sponsor, it results in any of the following outcomes:

- Death
- A life-threatening adverse event
- Inpatient hospitalization or prolongation of existing hospitalization
- A persistent or significant incapacity or substantial disruption of the ability to conduct normal life functions.
- A congenital anomaly/birth defect.

Important medical events that may not result in death, be life-threatening, or require hospitalization may be considered a serious adverse drug experience when, based upon appropriate medical judgment, they may jeopardize the patient or subject and may require medical or surgical intervention to prevent one of the outcomes listed in this definition. Examples of such medical events include allergic bronchospasm requiring intensive treatment in an emergency room or at home, blood dyscrasias or convulsions that do not result in inpatient hospitalization, or the development of drug dependency or drug abuse (21 CFR 312.32).

- Important medical events as defined above, may also be considered serious adverse events. Any important medical event can and should be reported as an SAE if deemed appropriate by the Principal Investigator or the IND Sponsor, IND Office.
- All events occurring during the conduct of a protocol and meeting the definition of a SAE must be reported to the IRB in accordance with the timeframes and procedures outlined in "The University of Texas M. D. Anderson Cancer Center Institutional Review Board Policy on Reporting Adverse Events for Drugs and Devices".
- Serious adverse events will be captured from the time of the first protocol-specific intervention, until 30 days after the last dose of drug, unless the participant withdraws consent.
- Serious adverse events must be followed until clinical recovery is complete and laboratory tests have returned to baseline, progression of the event has stabilized, or there has been acceptable resolution of the event.
- All SAEs, expected or unexpected/initial or follow up, must be reported to the IND
  Office within 5 working days of knowledge of the event regardless of the
  attribution.
- Death or life-threatening events that are unexpected, possibly, probably or definitely related to drug must be reported (initial or follow up) to the IND Sponsor within 24 hours of knowledge of the event
- Additionally, any serious adverse events that occur after the 30-day time period
  that are related to the study treatment must be reported to the INDSponsor. This
  may include the development of a secondary malignancy.
- The electronic SAE application (OnCore) will be utilized for safety reporting to the IND Sponsor and MD Anderson IRB.

Page | 42 04/25/2024

• All events reported to the supporting company must also be reported to the INDSponsor.

# 9.2.2.3. Reporting to Cellestia:

The investigator has to report the SAE to the supporting company of the study, Cellestia, within 24hr after becoming aware of the event and regardless of the relationship. The Adverse Event Reporting Form must be completed and forwarded to HEMEX Pharmacovigilance.

Contact details for HEMEX Pharmacovigilance are as follows:

Email: [contact] [contact]

Please note there are no AEs of Special Interest listed in the IB.

#### **10. REGULATORY REQUIREMENTS**

**10.1. Informed Consent:** Before a subject's participation in the clinical study, the Investigator is responsible for obtaining written informed consent from the subject or legally acceptable representative after adequate explanation of the aims, methods, anticipated benefits, and potential hazards of the study and before any protocol specific screening procedures or any investigational products are administered. A legally acceptable representative is an individual or other body authorized under applicable law to consent, on behalf of a prospective subject, to the subject's participation in the clinical study. Consented subjects will be registered in the institutional database CORe.

The acquisition of informed consent should be documented in the subject's medical records, and the informed consent form should be signed and personally dated by the subject or a legally acceptable representative and by the person who conducted the informed consent discussion. The original signed informed consent form should be retained in accordance with institutional policy, and a copy of the signed consent form should be provided to the subject or legally acceptable representative.

Subjects must have signed and dated an IRB approved informed consent in accordance with regulatory and institutional guidelines. MD Anderson SOP 04 will be used to guide the consent process for any patients for whom English is not the preferred language. This written informed consent must be obtained before the performance of any protocol-related procedures that are not part of normal subject care.

**10.2. Independent Ethics Committee/Institutional Review Board:** A copy of the protocol, proposed informed consent form, other written subject information, and any proposed advertising material must be submitted to the IRB for written approval. The Investigator must submit and, where necessary, obtain approval from the IRB for all subsequent protocol amendments and changes to the informed consent form. The Investigator should notify the IRB of deviations from the protocol or serious adverse events occurring at the site. The Investigator will be responsible for obtaining annual IRB approval/renewal throughout the duration of the study.

**10.3. Subject Confidentiality and Data Security:** The Investigator must ensure that the subject's confidentiality is maintained. Additionally, this protocol is reviewed by the MD Anderson DSMC. Subjects should be identified by their study number only and should be kept in strict confidence by the Investigator. In compliance with ICH GCP Guidelines, it is required that the investigator and institution permit authorized representatives of the company, of the regulatory agency(s), and the IRB direct access to review the subject's original medical records for verification of study-related procedures and data. Direct access includes examining, analyzing, verifying, and reproducing any records and reports that are important to the evaluation of the study. The Investigator is obligated to inform and obtain the consent of the subject to permit named representatives to have access to his/her study-related records without violating the confidentiality of the subject.

Participant confidentiality and privacy is strictly held in trust by the participating investigator, their staff, the safety and oversight monitor(s), and the sponsor(s) and funding agency. This confidentiality is extended to the data being collected as part of this study. Data that could be used to identify a specific study participant will be held in strict confidence within the research team. No personally identifiable information from the study will be released to any unauthorized third party without prior written approval of the sponsor/funding agency, as applicable.

All research activities will be conducted in as private a setting as possible.

Protocol 2021-0547 4/25/2024

